#### 2. STUDY AIMS

Our overarching hypothesis is that in addition to improving insulin sensitivity (IS) via modulating hepatic gluconeogenesis metformin therapy will counteract the elevated cellular senescence in OSA patients using PAP, and thereby reduce tissue IR and dysfunction. Specifically, we propose that cellular senescence continues to persist and propagate in tissue of OSA patients undergoing PAP treatment. Therefore, anti-senescent therapeutics such as metformin would benefit OSA patients by improving tissue function and consequent metabolic profile. Notably, the role of increased cellular senescence in obesity- and age-related metabolic disorders is being increasingly recognized. 

To test our hypothesis, we will conduct a double-blind, placebo-controlled, randomized clinical trial in nondiabetic OSA patients (Apnea hypopnea index, AHI≥15 events/h, HbA1c<6.4%) (fig 1). All participants will be provided PAP therapy and adherence will be monitored via monthly compliance visits. In addition, participants will be randomized to receive either metformin (2g/day, n=10) or matching placebo (n=10) for 3 months. Study measures will be collected at 0 and 3 months to address the following specific aims:

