# 5.3 Exclusion Criteria

Study volunteers are ineligible to participate (or will be excluded from participating in this study) if they meet any of the following criteria:

- HbA1c > 6.4%.
- Severe or uncontrolled hypertension defined as systolic BP ≥180 mmHg and/or diastolic BP ≥110 mmHg on the average of three seated measurements after being at rest for at least 5 minutes.
- Significant cardiovascular, hepatic, renal, neurologic, or psychiatric disease as determined by the study physician.
- Pregnancy, breast feeding or planning pregnancy in the coming 4 months.
- Impaired renal function defined as eGFR <60ml/min/1.73m^2 (estimated with CKD-EPI method).
- Known hypersensitivity to metformin.
- Currently taking a glucose lowering or weight loss medications.
- Current PAP use or use of PAP in the past 6 months.
- Currently taking antihypertensive and lipid-lowering medications known to affect adipose tissue and skeletal muscle metabolism. For example, statins and drugs targeting renin-angiotensin system will not be allowed. However, use of diuretics, beta-blockers, alpha-blockers and calcium channel blockers may be allowed provided the participant is on a stable dose for at least 3 months prior to the study visit.
- Oxygen desaturation index <15 events/h of sleep.
- Any medication or condition that, in the opinion of the medical investigator, could interfere with the study outcomes or put the subject at risk by participating in the study.

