# **10. STUDY VISITS**

# 10.1 Visit 3 (Baseline)

Participants will arrive to PBRC for an early morning fasting visit. Body weight will be measured along with measurement of waist, hip, arm and neck circumference. Blood sample will be drawn, questionnaires will be administered, and if needed, urine pregnancy test will be conducted. Participants will be given a standard glucose drink (75g glucose) to consume while timed blood samples will be collected every 30 min for 2 hours to measure glucose, insulin and free fatty acids (FFA). An abdominal adipose tissue biopsy and a skeletal muscle biopsy will be performed. Participants will also undergo whole-body DXA to determine body composition. At the end of this visit, participants will be provided a monitor to measure 24-h ambulatory blood

pressure and study drug will be dispensed with appropriate dose and safety instructions. Lunch will be provided prior to discharging the participants.

Following this visit, we will provide the study participants with PAP therapy through standard on-line resources (ApneaMD). PAP devices will be given to the participants at PBRC. PI will obtain equipment serial number to monitor adherence. For the first 4-weeks, study personal will monitor PAP compliance weekly (on-line data). Thereafter, we will monitor compliance on a monthly basis. Appropriate PAP use will be encouraged via additional consults and/or mask replacement as needed.

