# **12 COMPENSATION**

Participants will receive *up to* \$300 for completion the study (\$100 for Visit 3, \$25 each for Visit 4 and Visit 5, and \$150 for Visit 6/ End-of-Study).

Participants will not be compensated for screening visits. Payment will be received via check requested from the LSU payroll department.

All eligible participants will be provided PAP equipment for the study duration and allowed to keep the equipment for continued OSA treatment after the study is completed. Participants would be advised to followup with a Sleep-board certified physician for clinical care.

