### 14.4.2 Statistical Analyses

The primary outcome is insulin sensitivity via Matsuda Index. We will use mixed effect linear models, accounting for correlation over time and treatment to assess outcome difference in metformin and placebo treated groups. Primary analysis will be conducted on all study participants who have taken one dose of the study drug and used CPAP for at least one night. Sensitivity analyses will be conducted on per-protocol sample of subjects adherent to the study interventions. Publications will acknowledge the limitation of small sample and any other weaknesses.

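### The primary analysis set requires a CPAP night that can only follow randomisation, and the supplied text names no analysis of everyone randomised (minor)

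*Combined protocol and SAP*

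**What the plan says.** Section 14.4.2 names two analysis sets. The primary analysis is to be "conducted on all study participants who have taken one dose of the study drug and used CPAP for at least one night". The second is narrower: "Sensitivity analyses will be conducted on per-protocol sample of subjects adherent to the study interventions". The supplied text names no intention-to-treat, full-analysis or all-randomised set. Section 14.4 says the analysis will follow a pre-specified statistical analysis plan, but no further text of such a plan is supplied.

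PAP is not the randomised comparison. Section 9 randomises metformin against placebo, while Section 2 states "All participants will be provided PAP therapy and adherence will be monitored via monthly compliance visits" and Section 12 adds "All eligible participants will be provided PAP equipment for the study duration".

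**The concern.** Randomisation protects a comparison of the groups as allocated. A condition that is met or failed after allocation, on a therapy that both arms receive, gives up part of that protection. A randomised participant with no CPAP night leaves the primary set even if a Month 3 Matsuda value exists, and no other analysis in the supplied text brings that person back.

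Section 14.4.1 says the trial is meant to establish effect sizes for a later power calculation. At least one of those estimates should rest on everyone who was randomised.

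**Working it through.** **Is the condition post-randomisation?**

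1. Table 1 (Section 7) lists randomisation, drug dispensing and provision of PAP at Visit 3.
2. Section 10.1 says that at the end of that visit "study drug will be dispensed with appropriate dose and safety instructions". On PAP it says "Following this visit, we will provide the study participants with PAP therapy through standard on-line resources".
3. Section 5.3 excludes "Current PAP use or use of PAP in the past 6 months". In practice, then, the qualifying night is one during the study.
4. The CPAP night is therefore observed after allocation, at about the time the study drug starts.

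**Who is dropped?** Only participants with zero CPAP nights or zero doses. Someone who uses CPAP once and then stops stays in. Anyone adherent to both interventions has at least one dose and one night, so the per-protocol set lies inside the primary set and cannot restore those dropped.

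**What could it do to precision?** The plan gives no figure for this rule to reproduce. It gives no rate of zero-night participants and no SD for the Matsuda index. The following is an illustration under stated assumptions, for a simple difference in means rather than the planned mixed model.

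Inputs: n = 10 per arm (Section 2); outcome in SD units. Assumed: k = 1 or 2 never-starters, each differing by d SD from the rest and falling at random across the arms, all with a Month 3 value.

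Variance of the difference, all randomised:
- k = 1: 2/n + d²(1/n)² = 0.2000 + 0.0100d²
- k = 2: 2/n + p·d²(2/n)², where p is the chance that both fall in one arm. p = 2·C(10,2)/C(20,2) = 90/190 = 0.474, giving 0.2000 + 0.01895d²

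Variance, restricted set:
- k = 1: 1/10 + 1/9 = 0.2111, SE 0.459
- k = 2: 0.474(1/10 + 1/8) + 0.526(2/9) = 0.2235, SE 0.473

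| Offset d | k | SE, all randomised | SE, restricted | Restricted relative to all |
|---|---|---|---|---|
| 0 | 1 | 0.447 | 0.459 | 2.7% larger |
| 0 | 2 | 0.447 | 0.473 | 5.7% larger |
| 1 | 1 | 0.458 | 0.459 | 0.3% larger |
| 1 | 2 | 0.468 | 0.473 | 1.0% larger |
| 2 | 1 | 0.490 | 0.459 | about 6% smaller |
| 2 | 2 | 0.525 | 0.473 | about 10% smaller |

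The two are equal at d = √(0.0111/0.0100) ≈ 1.05 for k = 1, and at d = √(0.0235/0.01895) ≈ 1.11 for k = 2. With k = 0 the sets are identical. Precision therefore does not settle the choice.

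Both estimators are unbiased here only because exclusions were assumed random across arms. The calculation can neither show nor exclude bias.

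**Dilution in an all-randomised analysis.** If 1 of 10 on metformin never takes it and gets no effect, the arm's average effect is 9/10 of the full effect, about 10% lower.

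**The case against.** The strongest defence is that the rule fits the question. Aims 1 and 3 concern metformin together with PAP, and the overarching hypothesis in Section 2 is about patients using PAP. A one-night threshold is a recognisable modified intention-to-treat choice. The trial is a 20-person proof of concept. Willingness to use PAP is an inclusion criterion (Section 5.2), devices are handed over on site with weekly monitoring for four weeks (Section 10.1), and low users are interviewed and may be referred (Section 10.2). Zero-night participants may not occur at all. The one-dose condition is also post-randomisation, and the same blinding (Section 4.5) covers both conditions.

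Most of this stands, and it is why the point is minor. It does not justify the condition: one night does not secure a PAP-treated population, and the per-protocol set already addresses adherent use.

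Three stronger readings are tempting, and the documents support none of them.

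- **That the primary result will be biased.** Drug and PAP start close together, so a link between early tolerability and a first CPAP night is conceivable. No passage shows one, and double-blinding makes the expected bias small.
- **That the rule discards the CPAP-intolerant participants whom Section 4.6 keeps under follow-up.** That section covers people who stop CPAP. They will usually have had at least one night and so remain in the primary set. The documents do not say what follow-up a never-starter receives, so there may be no Month 3 value to lose.
- **That no all-randomised analysis was ever planned.** The plan mentioned in Section 14.4, if separate, might contain one.

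**Conclusion.** The point holds as a minor, inexpensive improvement. On the supplied text, the primary set applies a post-randomisation condition on therapy given to both arms, and no named analysis includes everyone randomised. That follows from reading the sections together and does not depend on the illustrative figures.

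The size is small and possibly nil. If one or two participants are affected, precision could move by a few percent up to about 10%, in either direction. Neither numerical harm nor a gain in precision is claimed. The case for the change is that it restores an as-randomised estimate for a trial meant to inform a later one.

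**What to change.** In Section 14.4.2, add an analysis of all randomised participants. Suggested wording: *An analysis will include all randomised participants as allocated, using all available Matsuda values regardless of CPAP use or number of doses taken. The numbers with zero CPAP nights and with zero doses will be reported by arm.*

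Preferably, also remove the CPAP-night condition from the primary set, and keep the current dose-and-CPAP set and the per-protocol set as supportive. The one-dose condition can stay in the primary set. When effect sizes are derived for the later power calculation (Section 14.4.1), show the all-randomised estimate beside the primary one. If a separate statistical analysis plan already defines such a set, aligning Section 14.4.2 with it is enough.

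The cost is wording only, with no new visits or measurements. The downside is slight dilution if someone never starts the study drug, and a small change in precision that could go either way. The supportive sets would show the effect of any zero-night participants.

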### 14.5 Data Sharing

- With Collaborators: There are no plans for any data sharing. If needed, data sharing agreements will be put into place with the collaborators prior to any data transfer. All shared data will be de-identified and occur over a secure, encrypted network.
- Sharing of Results with Participants: Clinically relevant incidental findings from questionnaires (excessive daytime sleepiness), overnight oximetry (risk for sleep apnea) and overnight sleep study will be shared with participants as determined by study MI.

